7.3.2. Incidence of Serious Adverse Events (SAEs)

- Name: Incidence of Serious Adverse Events (SAEs)
- Definition: Percentage of participants experiencing SAEs as defined by ICH GCP guidelines (death, life-threatening event, inpatient hospitalization, persistent or significant disability/incapacity, congenital anomaly/birth defect, or any other important medical event).
- Time Frame: Baseline to Day 10.
- Unit of Measure: Incidence (%).
- Assessment Method: Continuous monitoring, immediate reporting to IRB/DSMB, and documentation on CRFs.

7.3.3. Incidence of Withdrawals Due to Adverse Events

- Name: Incidence of Withdrawals Due to Adverse Events
- Definition: Percentage of participants discontinuing the study intervention or withdrawing from the study entirely due to an adverse event.
- Time Frame: Baseline to Day 10.
- Unit of Measure: Incidence (%).
- Assessment Method: Documented on CRFs, with reasons for withdrawal clearly recorded.

7.3.4. Incidence of Transient Diarrhea in Diabetic Participants

- Name: Incidence of Transient Diarrhea in Diabetic Participants
- Definition: The number of diabetic participants who experience transient diarrhea (defined as a temporary increase in stool frequency/looseness resolving spontaneously within 24-48 hours without requiring specific intervention or study withdrawal) during the first three days of the intervention.
- Time Frame: Days 1-3.
- Unit of Measure: Number of Participants.
- Assessment Method: Specific daily inquiry by investigators and recording in participant diaries and CRFs for diabetic participants.

8. Study Procedures and Schedule of Events

The study duration for each participant is 10 days of intervention, preceded by a screening period. All procedures will be meticulously documented.

- Day 2: Second Intervention Day
 - Participant Diary: Entry for Day 2.
 - Confirmation of study product administration.
 - Self-reported overall symptom severity (VAS 0-10).
 - Presence/absence and description of any AEs. Specific inquiry for transient diarrhea in diabetic participants.
 - Documentation: Daily diary entry collected/reviewed (or prepared for review at Day 3).
- Day 3: Mid-Intervention Assessment
 - Participant Visit: Brief in-person or remote contact.
 - Participant Diary Review: Investigator reviews Day 0-3 diary entries for completeness, symptom trends, and AE reporting. Queries participant regarding any unclear entries.

- Investigator Assessment: Clinician-assessed composite hemorrhoid severity score recorded. Specific inquiry about any gastrointestinal discomfort (nausea, bloating, etc.) and particularly for diabetic participants, the occurrence of transient diarrhea (Days 1-3) and its resolution.
- Concomitant Medications: Review of any new medications initiated since Day 0.
- Documentation: Day 3 CRFs completed, documenting investigator assessments and AE review. Diary entries for Day 0-3 collected.
- Day 4, Day 5, Day 6, Day 7, Day 8, Day 9: Ongoing Daily Intervention
 - Participant Diary: Daily entries for each respective day.
 - Confirmation of study product administration.
 - Self-reported overall symptom severity (VAS 0-10).
 - Presence/absence and description of any new or ongoing AEs.
 - Investigator Review: Optional periodic remote check-ins to monitor participant well-being and adherence. Document any AEs reported.
 - Documentation: Daily diary entries maintained by the participant for later collection/review at Day 10. For Day 7, if a remote check-in occurs, relevant CRFs are updated.
- Day 10: Final Assessment & Study Completion
 - Participant Visit: In-person final assessment.
 - Study Product Return & Pill Count: All remaining study capsules (both dispensed and unused) are collected and counted to calculate adherence.
 - Participant Diary Collection & Review: The complete participant diary (Day 0-10) is collected. Investigator performs a thorough review for completeness, consistency, symptom trends, and detailed AE reporting across the entire 10-day period. Any discrepancies or unclear entries are resolved with the participant.
 - Investigator Assessment:
 - Final clinician-assessed composite hemorrhoid severity score recorded.
 - Assessment of overall clinical improvement.
 - Physical examination (DRE/Anoscopy) repeated to evaluate physical signs of hemorrhoid regression. Post-treatment hemorrhoid images captured.
 - Adverse Event Review: Comprehensive review of all AEs experienced throughout the study, assessing severity, causality, and outcome. All AEs are documented on CRFs. Particular attention is given to SAEs.
 - Concomitant Medications: Final review and documentation of any changes in concomitant medications.
 - Study Completion: Participants completing all study procedures are considered study completers. Reasons for early withdrawal (if any) are documented.
 - Documentation: All collected data rigorously recorded in Day 10 CRFs.

8.3. Post-Treatment Follow-up While the primary intervention and assessment period concludes on Day 10, participants will be informed about the optional 6-month long-term follow-up study (Protocol NA-2024-02), which will assess recurrence rates, long-term safety, and quality of life. This is for future study planning and not part of the current protocol's scope, beyond informing participants.

9. Data Management and Quality Control

9.1. Data Collection Instruments (CRFs, Diaries)

- Case Report Forms (CRFs): Standardized, pre-printed CRFs will be used for all investigator-collected data, including eligibility, demographics, medical history, physical examinations, symptom assessments, adverse events, concomitant medications, and study product accountability. CRFs will be designed for clarity and ease of data entry. (Refer to Appendix A for CRFs).
- Participant Daily Diaries: Designed for self-reporting of daily symptom severity (VAS), adherence, and occurrence of AEs. Diaries will be simple, clear, and include instructions in the local language. (Refer to Appendix B for Participant Daily Diary).

9.2. Data Entry and Validation

- Data from CRFs and participant diaries will be entered into a secure, validated electronic data capture (EDC) system.
- Double Data Entry: A subset of CRFs (10%) may undergo double data entry by independent personnel to ensure accuracy.
- Data Validation Checks: The EDC system will incorporate automated validation checks for data range, consistency, and completeness (mandatory fields, logical checks between related variables).
- Query Management: Discrepancies identified during data entry or validation will generate queries that are sent back to the study sites for resolution by the investigator. All queries and their resolutions will be documented.

9.3. Data Quality Assurance

- Training: All study personnel involved in data collection and management will receive comprehensive training on the protocol, CRFs, EDC system, and GCP principles.
- Monitoring Visits: Study monitors will conduct regular on-site or remote monitoring visits to ensure adherence to the protocol, data accuracy, and regulatory compliance.
- Audits: Independent audits may be conducted by the sponsor or regulatory authorities to assess overall study conduct and data integrity.

9.4. Source Data Verification

- A percentage of data points (100% of primary and safety outcomes, 20% of secondary outcomes) will be verified against original source documents (hospital records, clinic notes, laboratory reports) to confirm accuracy and completeness.

9.5. Data Security and Confidentiality

- All participant data will be handled with strict confidentiality in accordance with applicable data protection regulations (GDPR equivalents, local privacy laws).
- Participants will be assigned a unique study identification number, and all study-related documents will be de-identified where possible.
- The EDC system will have robust security measures, including password protection, access control, audit trails, and data encryption.
- Only authorized personnel will have access to study data. Physical documents will be stored in locked cabinets in secure locations.

10. Statistical Analysis Plan

10.1. Analysis Populations

- **Intention-to-Treat (ITT) Population:** All randomized participants will be included in the primary efficacy analysis, analyzed according to their assigned treatment group, regardless of actual treatment received or protocol deviations. This reflects a real-world scenario.
- **Per-Protocol (PP) Population:** A subset of the ITT population, including only participants who complete the study without major protocol deviations, who demonstrate acceptable adherence ($\geq 80\%$ of doses taken), and who have evaluable primary outcome data. This population will be used for sensitivity analyses to assess the robustness of the ITT findings.

10.2. Missing Data Handling

- **Primary Method:** Multiple imputation will be used for missing outcome data, assuming data are Missing At Random (MAR).
- **Sensitivity Analyses:** Last Observation Carried Forward (LOCF) or complete case analysis will be conducted as sensitivity analyses to assess the impact of different missing data assumptions.

10.3. Statistical Software and Significance Level

- Statistical analyses will be performed using validated statistical software packages (SAS, R).
- All statistical tests will be two-sided, with a significance level (α) set at 0.05.

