7.2.3. Reduction in Individual Symptom Scores

- Name: Mean Reduction in Individual Symptom Scores (Bleeding, Pain, Itching, Swelling)
- Definition: Mean change from baseline to Day 10 for each individual symptom (bleeding, pain, itching, swelling) as assessed by the investigator using the 0-10 scale.
- Time Frame: Baseline to Day 10.
- Unit of Measure: Score (0-10 scale).
- Assessment Method: Clinician assessment via CRFs.

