7.2.4. Clinical Utility of the War-Drill Model

- Name: Association of War-Drill Model Classification with Treatment Response
- Definition: Evaluation of the association between initial classification (War Mode vs. Drill Mode) using the Parola Phenomenon and treatment response (hemorrhoid regression, symptom resolution) in both active and placebo arms.
- Time Frame: Classification at Baseline, outcomes at Day 10.
- Unit of Measure: Statistical association (Odds Ratio).
- Assessment Method: Clinical assessment for Parola Phenomenon at screening, correlated with primary and secondary outcomes.

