10.5. Secondary Outcome Analysis

- **VAS Symptom Score Change:** The mean change from baseline will be compared between groups using a Mann-Whitney U test due to potential non-normal distribution of symptom scores. The effect size will be reported as a Mean Difference with 95% CI. Baseline VAS scores may be included as a covariate in sensitivity analyses (ANCOVA).
- **Symptom Resolution Rate:** Compared between groups using a Chi-square test. The effect size will be reported as a Risk Ratio with 95% CI. Logistic regression may be used to adjust for baseline severity.
- **Individual Symptom Scores:** Mean changes will be compared using appropriate parametric (t-test) or non-parametric (Mann-Whitney U) tests based on data distribution.

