Statistical Analysis Plan (SAP): (Protocol NA-2024-01)

Official Title: Double-Blind, Placebo-Controlled, Parallel-Group Randomized Controlled Trial to Evaluate the Efficacy and Safety of Nimsai Herbal in Patients with Grade 2-3 Hemorrhoids

NCT Number: NCT07034820

Protocol Number: NA-2024-001

Document Date: October 10, 2021

Version: 2

Sponsor: Nimsai Academia Bursa, Türkiye

Principal Investigator: [name] Nimsai Academia

Center [contact]

Email: [contact]

Prepared by: Nimsai Academia Bursa, Türkiye

Submission Format: PDF/A

Confidentiality Statement: This document contains confidential information and is intended solely for authorized personnel, investigators, and regulatory authorities. Unauthorized reproduction or distribution is prohibited. No participant names or identifiable information are included.

1. Introduction

This Statistical Analysis Plan (SAP) outlines the detailed methodology for the statistical analysis of data collected during Protocol NA-2024-01, double-blind, placebo-controlled, parallel-group Randomized Controlled Trial evaluating the efficacy and safety of Nimsai Herbal in patients with Grade 2-3 hemorrhoids. This SAP is developed in conjunction with the study protocol (Protocol ID: NA-2024-01) and adheres to the principles of ICH Good Clinical Practice (GCP).

2. General Statistical Approach

- **Analysis Populations:** Analyses will be conducted on an intention-to-treat (ITT) basis, including all randomized participants regardless of treatment adherence or protocol deviations. A per-protocol (PP) sensitivity analysis will also be performed to assess the robustness of the primary findings, including only participants who completed the study as per protocol and had no major deviations.
- **Missing Data Handling:** Missing data for primary and secondary outcomes will be handled using appropriate methods, primarily multiple imputation if data are considered missing at random (MAR). Sensitivity analyses using Last Observation Carried Forward (LOCF) or complete case analysis will also be performed where appropriate.
- **Software:** Statistical analyses will be performed using validated statistical software, specifically SAS (Statistical Analysis System) or R.
- **Significance Level:** All statistical tests will be two-tailed, and a significance level of $\alpha=0.05$ will be used to determine statistical significance.

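### The secondary outcomes have no testing order, gating or alpha split: at an unadjusted 0.05 each, the chance of at least one false significant result is about 14–26% for the protocol's six tests and 8–10% for the SAP's two

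*Protocol*

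**What the plan says.** Both documents set one threshold for everything. Protocol 10.3: "All statistical tests will be two-sided, with a significance level (α) set at 0.05". SAP section 2 opens its rule with "All statistical tests will be two-tailed, and a significance level of" 0.05 and says that this level "will be used to determine statistical significance".

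Protocol 10.5 plans these between-arm secondary comparisons:

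- VAS change: "The mean change from baseline will be compared between groups using a Mann-Whitney U test".
- Symptom resolution: "Compared between groups using a Chi-square test. The effect size will be reported as a Risk Ratio with 95% CI".
- Individual symptom scores: "Mean changes will be compared using appropriate parametric (t-test) or non-parametric (Mann-Whitney U) tests based on data distribution". Protocol 7.2.3 defines these as bleeding, pain, itching and swelling, each scored separately, so this line is four tests.

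That makes six tests. SAP 3.2 lists only VAS change and symptom resolution, so its count is two.

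Protocol 7.2.4 adds a further secondary outcome, the "Evaluation of the association between initial classification (War Mode vs. Drill Mode) using the Parola Phenomenon and treatment response", with an odds ratio as its unit. Section 10.5 assigns it no test.

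Neither document gives a hierarchy, a condition on the primary result, an alpha allocation or a multiplicity adjustment. Protocol 10.8 calls the subgroup analyses hypothesis-generating. No such label covers the comparisons in 10.5.

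**The concern.** A threshold of 0.05 limits the error of one test. Here it is applied separately to several secondary outcomes, and any of them that crosses it meets the plan's own definition of statistical significance, whatever the primary shows. A significant difference in itching alone, with a failed primary, would qualify. The 5% rate does not hold for the set of secondary results taken together. Because the two documents disagree on what that set contains, a reader of the final report could not tell how many chances there were to find something.

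**Working it through.** **The plan's own figure.** The documents state no family-wise error for the secondaries. Their one related figure is power above 90% for the primary: 150 per arm, 50% vs 20%, two-sided 0.05 (Protocol 3.3, SAP 3.1). It reproduces. With pooled rate 0.35, the standard error under no difference is √(2 × 0.35 × 0.65 / 150) = 0.0551. Under the assumed rates it is √((0.50 × 0.50 + 0.20 × 0.80) / 150) = 0.0523. Then z = (0.30 − 1.96 × 0.0551) / 0.0523 = 3.67, so power is about 99.99%. This matters below for the cost of gating on the primary.

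**Inputs.** Per-test level 0.05, two-sided (Protocol 10.3, SAP 2). Number of secondary tests: six (Protocol 7.2.3 and 10.5) or two (SAP 3.2). Correlation between test statistics: not in the documents, so a range from 0 to 0.8 is assumed.

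**Independent tests.** The chance of at least one significant result when no effect exists is 1 − (1 − 0.05)^k.

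- Six tests: 1 − 0.95^6 = 1 − 0.7351 = 0.2649.
- Two tests: 1 − 0.95^2 = 1 − 0.9025 = 0.0975.
- Favouring the active arm only: 1 − 0.975^6 = 0.1409 and 1 − 0.975^2 = 0.0494, against 0.025 for one test.

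**Correlated tests.** Test statistics were simulated as normal with a common pairwise correlation (2,000,000 draws; Monte Carlo standard error at most √(0.265 × 0.735 / 2,000,000) = 0.0003). The either-direction columns count draws in which any statistic exceeds 1.96 in absolute value.

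| Assumed correlation | Six tests, either direction | Six tests, favouring active | Two tests, either direction | Two tests, favouring active |
|---|---|---|---|---|
| 0 | 0.2650 | 0.1410 | 0.0974 | 0.0493 |
| 0.3 | 0.2411 | 0.1211 | 0.0951 | 0.0476 |
| 0.5 | 0.2075 | 0.1037 | 0.0906 | 0.0452 |
| 0.7 | 0.1642 | 0.0821 | 0.0833 | 0.0415 |
| 0.8 | 0.1386 | 0.0694 | 0.0786 | 0.0393 |

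**Check with the trial's structure.** Equal correlation is a simplification, so whole trials were also simulated under no effect. Each had 150 per arm, four correlated symptom scores, a correlated VAS, and a resolution indicator derived from the sum of the four scores. With between-symptom correlations of 0.2 to 0.7 and assumed resolution rates of 5% to 20%, the chance of at least one significant result among the six was 0.169 to 0.247. Each single test rejected about 5% of the time, so the excess comes from the number of tests and not from a faulty test.

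**After the change.** In a fixed sequence a test is reached only if the one before it succeeded, so each step can use 0.05 and the chance of any false claim stays at or below 5%. Holm over the four symptoms starts at 0.05 / 4 = 0.0125 for the smallest p-value. At the sponsor's assumed rates the primary gate is passed about 99.99% of the time.

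**The case against.** The strongest reply is that secondary outcomes are commonly reported at a nominal 0.05 as supportive evidence. The trial has one primary outcome with one test, and neither document says that a secondary result would carry an efficacy claim if the primary failed. A reader might infer from the missing label that the secondaries are confirmatory. The documents do not use that word, and the inference goes too far. What remains is that the plan does not call them supportive either, and its only stated rule decides significance at 0.05 for each of them. A sentence labelling them supportive would also remove the problem, but there is none.

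Three objections to the size are fair and limit it:

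- The larger range depends on the protocol's list. Under the SAP's list the excess is modest.
- Independence is an outer bound. Resolution is a function of the four symptom scores, and the VAS rates the same condition, so the lower part of the range is more plausible.
- The main percentages count results in either direction. Those a sponsor would want to claim are about half as likely.

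A reader might also add the War-Drill outcome as four odds ratios (two responses in each of two arms), making ten tests and 1 − 0.95^10 = 40%. The documents do not support this. Section 10.5 plans no test for that outcome, Protocol 2.2 words the objective as exploratory, and 10.8 treats War versus Drill as hypothesis-generating when it is used as a subgroup. Odds ratios from the two arms come from different participants, so they would not share the common correlation assumed above.

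**Conclusion.** The concern holds for the secondary outcomes only. Following the rule as written, with no true secondary effect, gives about a 14–26% chance of at least one significant secondary result in either direction for the protocol's six tests, and about 8–10% for the SAP's two. For a false result favouring the active arm the figures are about 7–14% and 4–5%. All rest on assumed pairwise correlations between 0.8 and 0; above 0.8 they would be lower.

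It would be wrong to read this as inflation of the primary test, whose 5% error is intact. It gives no reason to alter the planned safety comparisons either. The weakness should be corrected because it governs which secondary results may be claimed; it does not threaten the primary conclusion.

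**What to change.** First reconcile the secondary list between Protocol 7.2 and 10.5 and SAP 3.2. Protocol 2.2 should be aligned as well, since it words the individual-symptom objective as a proportion while 7.2.3 uses a mean change.

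Then state one sequence in Protocol 10.3 and 10.5 and in SAP 2:

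1. Test the primary at 0.05.
2. Only if it is significant, test VAS change at 0.05.
3. Only if that is significant, test symptom resolution at 0.05.
4. Only if that is significant, test the four individual symptoms with Holm at 0.05.

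Stop claiming significance at the first failure. Report everything after it, and the War-Drill odds ratios, as exploratory with estimate and 95% CI. Leave the planned safety comparisons as they are.

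The sequence counts as prespecified only if it is fixed before unblinding. The documents do not show whether that is still possible: Protocol 3.2 ends the study period on 14 November 2021, and the reference list includes a 2025 item. If the data are already unblinded, report the secondary p-values as nominal and unadjusted.

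The cost is a few lines of text, with no extra participants and no loss of power for the primary. The real price is that a lone nominally significant secondary result may no longer be claimable.

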10.4. Primary Outcome Analysis

- **Hemorrhoid Regression Rate:** Compared between the Nimsai Herbal and placebo groups using a Chi-square test. The effect size will be reported as a Risk Difference with its 95% Confidence Interval (CI).

10.5. Secondary Outcome Analysis

- **VAS Symptom Score Change:** The mean change from baseline will be compared between groups using a Mann-Whitney U test due to potential non-normal distribution of symptom scores. The effect size will be reported as a Mean Difference with 95% CI. Baseline VAS scores may be included as a covariate in sensitivity analyses (ANCOVA).
- **Symptom Resolution Rate:** Compared between groups using a Chi-square test. The effect size will be reported as a Risk Ratio with 95% CI. Logistic regression may be used to adjust for baseline severity.
- **Individual Symptom Scores:** Mean changes will be compared using appropriate parametric (t-test) or non-parametric (Mann-Whitney U) tests based on data distribution.

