3.3. Enrollment and Sample Size

- Planned Enrollment: A total of 300 participants will be enrolled (150 in the Nimsai Herbal group and 150 in the placebo group).
- Sample Size Justification: A sample size of 150 participants per arm (total 300) provides >90% power to detect a 30% difference in hemorrhoid regression rate (assuming 50% regression in the Nimsai Herbal group vs. 20% in the placebo group) with a two-sided alpha level of 0.05. This calculation accounts for potential minor dropouts.

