3.2.2. Symptom Resolution Rate

- Name: Symptom Resolution Rate
- Definition: Percentage of participants reporting complete resolution of baseline hemorrhoid symptoms (pain, bleeding, itching, swelling), defined as a composite severity score of 0.
- Time Frame: Day 10
- Statistical Test: Chi-square test
- Method: Comparison of categorical data (proportion of participants with complete symptom resolution) between the Nimsai Herbal and placebo groups.
- Effect Size: Risk Ratio with a 95% CI.
- Adjustment: Logistic regression may be used to adjust for baseline hemorrhoid severity or other relevant covariates in supplementary analyses.

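### Symptom resolution is analysed without the baseline score and grade already collected, and its optional logistic adjustment has no stated covariate definition or effect measure; a pre-specified standardised risk ratio is a free improvement

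*Protocol*

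**What the plan says.** In Protocol 10.5 the main analysis of symptom resolution is an unadjusted chi-square comparison of the two arms, and the section continues: "The effect size will be reported as a Risk Ratio with 95% CI. Logistic regression may be used to adjust for baseline severity". SAP 3.2.2 names the same test and effect measure. Resolution means a Day 10 composite of 0 on the 0-40 scale (Protocol 7.1 and 7.2.2).

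Adjustment is optional in both documents. The SAP makes it supplementary and widens it: "Logistic regression may be used to adjust for baseline hemorrhoid severity or other relevant covariates in supplementary analyses". Neither document says what effect measure the adjusted model will report or how a risk ratio would be obtained from it.

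Three other places matter:

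- Protocol 8.2 records the investigator-assessed composite at Day 0.
- Protocol 6.1 stratifies randomisation by Grade 2 v Grade 3 and calls that grading severity, while Protocol 7.1 uses severity for the composite score.
- SAP 3.2.1 accepts, for the VAS outcome, that adjusting for baseline can improve precision.

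**The concern.** Resolution requires a score of exactly 0, and Protocol 4.1 sets no minimum baseline score. It is plausible, though not documented, that a participant who starts low reaches 0 more easily than one who starts high. If so, the baseline composite carries information that the main analysis does not use. Grade is balanced by design and then left out of the analysis.

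The optional adjustment does not fill this gap. Two analysts could fit different models, one with grade and one with the score, and both would comply. Whether to adjust, and for what, can be settled after the data are seen. The baseline significance tests in Protocol 10.7 and SAP section 4 could prompt that choice. If the treatment coefficient is reported as it comes out of the model, the adjusted result will be a conditional odds ratio beside an unadjusted risk ratio, and the sizes of the two cannot be compared directly.

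**Working it through.** **The plan's own figure.** The only power statement concerns the primary outcome. Protocol 3.3 says that the planned enrolment "provides >90% power to detect a 30% difference in hemorrhoid regression rate". The rates behind it are 50% on active and 20% on placebo. With n = 150 per arm, two-sided α = 0.05 and pooled rate 0.35:

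z = [0.30 − 1.96·√(2·0.35·0.65/150)] / √[(0.5·0.5 + 0.2·0.8)/150] = (0.300 − 0.108)/0.0523 = 3.67, so power is 0.9999.

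The claim of more than 90% is met. The documents give no rate, effect or power for resolution. A participant who goes from a positive baseline to 0 also meets the primary criterion of a 75% reduction, so resolution cannot be more frequent than regression. The pair 50% v 20% is therefore an upper bound for each arm, if the primary assumptions are right. All resolution rates below are assumptions.

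**Step 1. Risk ratio against unadjusted odds ratio.** RR = p1/p0; OR = [p1/(1−p1)]/[p0/(1−p0)]; so OR/RR = (1−p0)/(1−p1).

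| Active v placebo | RR | OR | OR above RR by |
|---|---|---|---|
| 50% v 20% | 2.50 | 4.00 | 60% |
| 40% v 15% | 2.67 | 3.78 | 42% |
| 30% v 10% | 3.00 | 3.86 | 29% |
| 20% v 10% | 2.00 | 2.25 | 12.5% |
| 10% v 5% | 2.00 | 2.11 | 6% |
| 5% v 2% | 2.50 | 2.58 | 3% |
| 20% v 20% | 1.00 | 1.00 | 0% |

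**Step 2. What adjustment does.** Simulation with 150 per arm and 2,000 trials per scenario. One standardised baseline covariate x follows a normal distribution, and logit P(resolution) = a(arm) − b·x. The intercepts are solved so that each arm's overall rate stays at the assumed value. The slope b (log-odds per SD) is assumed. Allocation is simple 1:1; grade was not simulated. Each trial gives the unadjusted RR and a standardised RR, which is the mean predicted risk with everyone set to active divided by the mean with everyone set to placebo. The table shows the conditional OR implied by the model, then the ratio of the variance of the standardised log RR to that of the unadjusted log RR.

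| Rates | b = 0 | b = 0.5 | b = 1.0 | b = 1.5 |
|---|---|---|---|---|
| 50% v 20% | 4.00; 1.004 | 4.30; 0.967 | 5.20; 0.881 | 6.78; 0.751 |
| 30% v 10% | 3.86; 1.004 | 4.06; 0.985 | 4.69; 0.920 | 5.84; 0.813 |
| 20% v 10% | 2.25; 0.998 | 2.31; 0.983 | 2.50; 0.908 | 2.82; 0.793 |
| 20% v 20% | 1.00; 1.002 | 1.00; 0.959 | 1.00; 0.871 | 1.00; 0.737 |

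- *Scale.* The median standardised RR stays on target: 2.49-2.51 when the truth is 2.5, 3.00-3.03 for 3.0, and 1.99-2.03 for 2.0. The conditional OR moves further from 1 as the covariate becomes more prognostic.
- *Precision.* The variance of the log RR falls by about 0% at b = 0, 2-4% at 0.5, 8-13% at 1.0 and 19-26% at 1.5. At the largest gain the confidence interval is about 14% narrower on the log scale (1 − √0.737 = 0.14).
- *Power at 20% v 10%.* Chi-square 0.67-0.69 throughout; adjusted Wald test 0.68, 0.69, 0.72 and 0.78 as b rises.
- *Type I error at 20% v 20%.* Adjusted test 0.042-0.048, so adjustment does not inflate it.

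**The case against.** The strongest reply is that nothing planned here is wrong. In a randomised trial with 150 per arm, the unadjusted chi-square and risk ratio are valid for the marginal effect and hold their error rate. Resolution is a secondary outcome, the SAP calls the adjustment supplementary, and the primary result is untouched. All of that stands.

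A reader might go further than the text in three ways, none of which it supports:

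- *That the plan replaces the risk ratio with an odds ratio.* It does not say so. The only measure named for resolution is the risk ratio; an odds ratio is named only for the War-Drill association in Protocol 7.2.4. A logistic model can also yield a risk ratio. The gap is an unstated measure.
- *That the adjusted effect will look larger than the true one.* An odds ratio is correct on its own scale and misleads only if read as a risk ratio. In the unadjusted comparison, the difference is about 3-6% in the examples where resolution is 10% or less, and nil with no effect.
- *That the two analyses cannot check each other.* They can be compared on direction and p-value; only the sizes are not directly comparable.

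The reply also correctly says that the precision gain cannot be fixed from the documents. If baseline score is weakly prognostic, the gain is close to zero.

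Two things remain: available baseline information goes unused, and the only adjustment on offer is open as to whether it is done, with which covariates and on which scale.

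**Conclusion.** The point holds as a free improvement, not as an error in the main analysis. Adjusting for the baseline composite and reporting a standardised risk ratio keeps the planned scale. In the simulation, adjusting for a baseline score lowered the variance of the log risk ratio by about 0% to 26%. That range depends wholly on assumed slopes of 0 to 1.5 per SD and assumed resolution rates, and any further contribution from grade was not quantified. How far an odds ratio could mislead depends on the same unknowns: large near 50% v 20%, slight when resolution is uncommon. Specifying the adjusted analysis in advance also removes a choice that could otherwise be made after the results are known.

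**What to change.** In SAP 3.2.2, and to match in Protocol 10.5:

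1. Make the planned analysis of resolution a logistic model with arm, Day 0 composite score (continuous) and grade (2 v 3).
2. Report the risk ratio by standardisation: average the predicted risks with all participants set to active, then to placebo, and take the ratio. Give a delta-method or bootstrap 95% CI. With the planned multiple imputation, do this in each imputed data set and combine on the log scale.
3. Keep the chi-square and unadjusted risk ratio as supportive results. Name them as the fallback if the model does not converge; at 5% v 2%, for example, only about 7.5 and 3 events are expected (150 × 0.05 and 150 × 0.02).
4. Delete the open clause on other covariates, and replace the undefined severity term with the two named variables.

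The cost is a few lines of SAP wording and code. Both covariates are already collected, so there are no new visits, data or participants. The wording has to be fixed before unblinding to count as pre-specified.
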